SMASH AA Kidney Transplant Patients with HTN Trial #1: We first ran a 3-mo feasibility RCT in 20 AAs with uncontrolled HTN who were also kidney transplant recipients. They were verified as having uncontrolled BP from clinic records followed by a BP screening. Majority had med possession ratios (MPRs) >0.85. Thus, we identified patients as nonadherent (i.e., adherence score <0.85) to their med regimen based on a month-long screening using an electronic med tray (Maya MedMinder™) with reminder functions disabled. We used a modification of Russell et al.'s algorithm⁵² [see Appx. 2]) which considers dose timing in addition to dose taking, especially important when taking meds with especially short half-lives.^{20,21} We modified the algorithm to allow for dosing schedules other than twice daily. Subjects were instructed that to be fully adherent, their meds had to be taken within a 3 hr window centered on the prescribed dosing time (within 90 min before or 90 min after designated time.) A dose taken within the 3 hr window resulted in a full score for that dosing time; a dose taken outside the 3 hr window but within 6 hr window resulted in a half score for that dosing time; a missed dose resulted in a score of 0. Each subject received a score from 0-1.0 per day and scores averaged over the month. Despite self-reporting high MA, having MPRs often ≥0.85 for previous month and knowing their exact times of intake were being monitored, they had a mean adherence score of 0.63 (range 0.26-0.94.) Seventy-

Demographic	Transplant (N=46)	Stroke (N=27)	FQHC (N=66)	Average
Age (avg.)	54.2	52.9	53.4	53.5
Own Mobile Phone (%)	97.8	92.6	87.0	91.1
Own Smart phone (%)	47.6	51.8	51.3	50.6
Help at home (%)	82.2	81.5	77.1	79.5
SMS Text (%)	65.2	77.8	60.0	67.7
Email (%)	32.6	29.6	40.0	34.1
Internet surfing (%)	34.8	40.7	32.5	36.0
Download apps (%)	43.5	40.7	42.5	42.2
Medication Adherence Self-Report				
Missed dose in last 2 weeks (%)	4.0	25.0	64.4	31.1
mHealth opinion				
Receptive to using (%)	80.4	85.2	92.5	86.0
Knew of mHealth (%)	8.7	7.4	16.2	10.8
Follow Dr.'s orders (%)	76.0	92.6	90.0	86.2
Dr. make more timely med change (%)	84.8	88.9	90.0	87.9

[figure not shown]
nine % of those screened were deemed non-adherent (i.e., MedMinder adherence score <0.85).^{22,23}

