D.3.b. MNA Identification Phase: Subjects will be shown how MedMinder™ works and demonstrate proficiency in loading and activating the device. They will be told their doctors will receive summary reports on their med intake patterns. The tray plugs into a standard 110v outlet, has 28 compartments allowing up to 4 dose times per day for 7 days, and is capable of providing escalating reminder signals (described in D.5.a). **Reminder functions will be disabled for the 1-month screening phase.** The nurse manager (or project manager, [name]) and subject will program the MedMinder for dosing times (example of subject's 24-hr MedMinder activity in Appx. 23). Subject will receive written and oral instructions on MA criteria (i.e., all meds taken within 180 min window centered on prescribed dosing time). SMASH app has auto call feature for TACHL service line for technical issues. Time and date stamped opening and closure of the tray's compartments are relayed via GSM wireless cellular transmitter/receiver to MedMinder™ server for processing. The encrypted data are sent to a HIPPA-compliant server database housed in the TACHL center. The MA formula will be used to calculate MA scores.^{22,23,52,121} (see Appx. 2) **Only subjects with MA score < 0.85 over the 4 week screening and whose subsequent resting and 24-hr SBP evaluations reconfirm uncontrolled HTN will be eligible for enrollment into the RCT.** [name] will randomly assign the 8 sites to either SMASH or

enhanced SC conditions.

D.4. Time Table (Table 2) Based on our SMASH trials, we will recruit 16 subjects/mo beginning mo 4 and finish recruiting by mo 15. We will provide a smart phone and/or service plan for ~40 SMASHers we project might lose phones or service plans during the trial.^{20,21,25,27} Post-trial data collection will finish in mo 34. Post study focus groups and subsequent qualitative analyses will end in mo 43. Table 2 presents a timetable for the study.

Activity	Month
Set-up	Mos 1-3
Recruitment	Mos 4-15
Intervention	Mos 5-22
Follow-up	Mos 16-34
Focus Groups	Mos 35-37
Statistical analyses	Mos 23-28
Prep. and Submission of Effectiveness RCT RO1	Mos 36-42
	Mos 43-48
Month	0 2 4 6 8 10 12 14 16 18 20 22 24 26 28 30 32 34 36 38 40 42 44 46 48
Year	1 2 3 4

D.5. SMASH Protocol:

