SDT constructs	TSRQ Autonomous Self-Motivation (α .81-.84)(Appx.8) ^{97,122} Perceived Competence Scale (MASES-R) (.92, test-retest [3 mos.] .51) (Appx.7). ^{101,123,124}	Baseline,3,6,12,18 mos
Exploratory Outcomes		
Cost effectiveness	Costs of additional personnel time, SMASH devices, ED visits, unplanned outpatient visits & hospitalizations, workdays lost.	First 6 mos of trial & through post-trial follow-ups
Physical Risk Factors	TC, LDL, HgA1c, blood glucose from FQHC standard care via MedCorp (intra-assay variations all <5%; inter-assay variations 3.3% to 6.6%)	Baseline,6,12,18 mos
Potential MA Mediators	HTN Knowledge (.70) (Appx.9); ^{129,130} Short Test of Functional Health Literacy (S-TOFHLA)(.68) (Appx.10); ¹³¹⁻¹³³ SF-8(α .87) (Appx.12); ¹³⁵ Med Side effects (Appx.11); ¹³⁴ Adverse events; Pittsburgh Sleep Quality Index (sleep quality) (.83; test-retest [1mo, 12 mo] .85, .68) (Appx.16); ^{138,139} Beck Depression Inventory (BDI) (0.82-0.92); (Appx.13); ¹¹³⁻¹¹⁵ Perceived Stress Scale (PSS) (.84-.86; test-retest [2 day] .85)(Appx.15); ^{136,137} Illness Perception Questionnaire (IPQ-R; perceived disease severity); .84, test-retest [3 weeks,6 mos] .74.,.74) (Appx.17); ¹⁴⁰ Questionnaire on Quality of Patient & Physician Interaction (QQPPI)(Appx.18). ¹⁴¹	Baseline,3,6,12,18 mos
Values/Beliefs/Goals	Values, Beliefs, Goals (test-retest [1 mo].85) (Appx.14). ¹⁰⁶	Baseline,3,6,12,18 mos
Anthropometrics	Ht./Wt./Girth (Appx.6).	
Sociodemographics	Age, education level, income, type of healthcare insurance	Baseline
Feasibility	Recruitment and Retention rates.	End of trial
System Usability	System Usability Scale (Appx. 19); ^{146,147} Patient/Provider SMASH/SC Treatment Satisfaction & Usability Scale (TSUQ) (α .82-.96, test-retest [1wk] .98) (Appx.20); ^{144,145} User Version of Mobile App Rating Scale (uMARS) (.90, test-retest [2, 3 mos] .66, .70) (Appx.21). ^{142,143}	At 6 mos (All subjects) After all subjects complete 6 mos trial (Providers)
Process/uptake	Patient level (e.g., connection/reloads of MedMinder, BP uploads via phone & opening of messages /education info) & provider level (e.g., opening of patient summary reports & phone alerts).	First 6 mos of trial

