Cochran-Mantel-Haentzel chi-square tests of differences in % of patients being >0.90 med adherent and % of patients within JNC8 guidelines for BP control (<140/90 mmHg) at the 6 month visit (primary endpoint) between the two groups (SMASH; enhanced SC). Type I error rate was 0.05 (two-sided). Sample size was adjusted to account for the cluster randomization scheme, using variance inflation factor (VIF) method.¹⁴⁸ Power and sample size estimates were performed for within-clinic sample sizes of 22 subjects for 4 clinics per group, assuming ICCs ranging from 0.0 to 0.05. The ICC from our feasibility trials for primary outcomes of electronic med tray based MA and SBP was estimated at 0.04. For an ICC of 0.04 the proposed sample size of 22 per clinic and 4 clinics per group provides at least 90% power to detect a difference in the assumed 6-month MA/BP control rates between the 2 groups (difference of $\geq 30\%$ between SMASH and SC based on feasibility trials' results).^{22,23,25,26} For the proposed study, for calculation of the VIF we used the conservative absolute ICC value of .04 for a final sample size 176. We inflated that by 10% (N=192) to account for greater than expected attrition across the trial. Conservative estimates for expected MA (or BP control) proportions were used for power calculations; proportions observed in our SMASH feasibility studies were 89% vs. 0%, N=19 for MA based upon MedMinder^{22,23} and for resting SBP, an average of 90% vs. 10% for the three trials lasting 3 and 6 months and the recent 12-month follow-up (n=19,²² n= 22,²⁵ n= 24,²³ n=19,²²). For secondary continuous outcomes of 24-hr BP (and MPR derived MA scores) for longitudinal analyses [assuming 4 intervention time points (months 3, 6, 12, and 18), level of significance = 0.05 (two-tailed), correlation among repeated measures (ICC ≤ 0.5)], we will have 90% power to detect a 0.48 standardized effect size (i.e., Cohen's d effect size). A standardized effect size of 0.48 sd is equivalent to a raw effect size ranging from 2.4 to 4.3 mmHg (raw scale units) for difference in SBP change from baseline between the groups for a range of sd from 5.0 to 9.0 mmHg, based upon our SMASH feasibility data.^{22,23,25,26} For resting DBP based upon our SMASH findings, this equates to a difference of 1.3 to 3.3 mmHg assuming sd ranging from 2.0-5.0 mmHg. SMASH findings for the tray derived monthly MA scores revealed a difference in MA score changes between the groups from baseline to 3 month of 28% (sd=6.2).^{22,23} Assuming similar adherence in both groups through the 6-month trial, we will have at least 94% power to detect differences in adherence change scores as small as 10% (with sd up to 15).

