D.10. Quantitative Analyses: AIM1 Primary outcome measures are % of subjects with >0.90 MA from MedMinder and % within JNC8 clinic resting BP guidelines (<140/90 mmHg). Secondary analyses will assess resting & ambulatory BP levels (e.g., 24-hr, daytime/nighttime BP level changes) & MA indices (i.e., MPR score changes). Intent-to-Treat (ITT) sample analyses will be used along with multiple imputation methods for missing end-of-study outcomes.^{149,150} To assess relationships between intervention outcomes and intervention status (SMASH or SC) at end of the active trial period (6-mo visit, primary endpoint), two-sided Cochran-Mantel-Haentzel chi-square tests for unadjusted differences in proportions will be used. Adjusted differences in proportions at the 6-mo visit will be compared using logistic regression. To assess relationships over time, we will use a generalized linear mixed models (GLMM; generalized estimation equation [GEE]-type models) analytic model with group (SMASH vs SC) & time (3, 6, 12 & 18 months) included as fixed effects and FQHC practice site as a random effect to account for clustering within FQHC practice site/MD.¹⁵¹⁻¹⁵³ In the first set of models, baseline measurement of the dependent variables (e.g., MA or BP levels) will be included as adjustment variable. The test of primary interest is F-test for the treatment x time interaction, which will reflect a difference in change between the 2 groups over the study. If a statistically significant treatment x time

interaction is found, we will obtain odds ratios for SMASH vs SC groups at each of the study time points.

A mixed effects model (MEM) will be used to compare the primary continuous outcome measures (e.g., tray or MPR derived MA scores or BP levels) for the two groups over the study period. Modeling will be carried out as described above. We will estimate resting and 24-hr BP changes and MA (MPR) changes for each subject over the trial (baseline, 3, 6, 12 & 18 months) and the within subject longitudinal trajectories (e.g., slopes) and summarize as the mean longitudinal trajectory within each group. ICCs and variance estimates will be obtained of efficacy outcomes and covariance structure of the longitudinal scores for determination of sample size (and hence adequate power) for a future effectiveness RCT.

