scores, mobile app usability scale score). These results will be used in exploratory structural equation modeling with outcomes of sustained MA and BP control. Those findings will further guide SMASH refinement for a future effectiveness RCT. Dropout rate is an important issue. We will assess reasons for dropout and compare groups for missing outcome measures using logistic regression modeling. If >10% of data are missing, we will likely add an intermediate evaluation point in a future RCT to provide more data for use in endpoint imputation. Frequency distributions of adverse events & serious adverse events will also be obtained. Proportions within categories of AEs/SAEs for the SMASH vs. SC will be compared via chi-square analyses.

D.11. Qualitative & Mixed Methods Analyses: As in our other recent studies,¹⁵⁹⁻¹⁶³ we will use the constant comparative method of qualitative analysis derived from constructivist grounded theory.^{164,165} This approach acknowledges researchers' prior knowledge and influence in the process, supports and provides guidelines for building a conceptual framework to understand interrelations (e.g., what and how) between constructs. NVivo 11 will be used to identify common themes constructs regarding MA, BP self-monitoring, etc. Iterative coding will be conducted by [name] to identify thick descriptors of informants' responses, refine theme classifications, and impose a data-derived hierarchy of nodes. Interrelations between individual classifications (e.g., gender, age, responder vs partial/non responder) and themes will be examined for relationships. To evaluate reliability and validity of the conclusions, [name] will code a random selection of 20% of these cases and conduct member checks to ensure validity of the findings. Drs. [name] and [name] will use reflection and a process of immersion and crystallization¹⁶⁶ to reconcile any differences and reach consensus. Once no new themes emerge, thematic saturation will have been reached,¹⁶⁷ We will compare and contrast themes from participants and providers. The quantitative and qualitative data sources will be analyzed in a mixed methods sequential triangulation approach.¹⁶⁸ We will refine SMASH content, delivery format and feedback mechanisms for initial and sustained use, based on participants' adherence data, responses to feedback, providers' responses and other variables that might influence optimal use of SMASH.^{169,170}

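### Missing 6-month primary outcomes are multiply imputed with no check against dropout related to adherence, and the trigger at more than 10% missing changes only a future trial

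*Combined protocol and SAP*

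**What the plan says.** All references are to the combined protocol and SAP.

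- **Outcome.** D.10, AIM 1: "Primary outcome measures are % of subjects with >0.90 MA from MedMinder", alongside the share with resting BP under control. The 6-month visit is the primary endpoint for both.
- **Missing data.** D.10, AIM 1: intent-to-treat "sample analyses will be used along with multiple imputation methods for missing end-of-study outcomes". No imputation model, predictors or missingness assumption is given. The only sensitivity analyses in the plan concern costs.
- **Dropout.** D.10, end of the mediation paragraph: reasons for dropout are reviewed and the arms are compared on missingness by logistic regression. Then: "If >10% of data are missing, we will likely add an intermediate evaluation point in a future RCT".
- **Scoring.** C.1.4, describing feasibility trial 1: "a missed dose resulted in a score of 0", and "Each subject received a score from 0-1.0 per day and scores averaged over the month". For this trial D.3.b says "The MA formula will be used to calculate MA scores" and points to Appendix 2, which is not in the supplied text.
- **Data that could help.** Table 3 lists, as process measures, "connection/reloads of MedMinder, BP uploads via phone". It also lists daily tray data for 6 months and resting BP at month 3.
- **Attrition allowance.** D.8, starting from 176: "We inflated that by 10% (N=192) to account for greater than expected attrition across the trial".

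**The concern.** Patients who give up the tray or leave the study are unlikely to be a random sample with respect to adherence. Multiple imputation as usually run assumes that, given the variables in the model, missing patients resemble observed ones. The plan does not state this assumption, and nothing in it tests how far the result depends on it. The arm comparison of missingness may show a problem, but no finding from it changes an analysis of this trial.

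The tray outcome has a second gap. Compartment openings reach the server by cellular transmission (D.3.b), so a skipped dose, an unplugged tray and a signal outage might all appear as no opening. The supplied text does not say which of these score 0 and which are missing. With a cutoff at 0.90, a short silent period can change a patient's classification. If the rule is chosen after results by arm are visible, the choice could be driven by the outcome.

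**Working it through.** **1. The plan's own figure.** Inputs from D.8 and D.1: 176 before attrition, a 10% allowance, 8 clinics of 24.
- 8 x 24 = 192. Adding 10% gives 176 x 1.10 = 193.6; dividing by the retained share gives 176 / 0.90 = 195.6, so 196. The stated 192 is close to both.
- Loss that leaves exactly 176: (192 - 176) / 192 = 8.3%. At 10% loss, 192 x 0.90 = 172.8 remain.
- Effect on information at ICC 0.04: planned, 88 / (1 + 21 x 0.04) = 88 / 1.84 = 47.8 effective patients per arm. At 10% loss there are 21.6 per clinic, so 86.4 / (1 + 20.6 x 0.04) = 86.4 / 1.824 = 47.4. The shortfall is trivial.

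**2. Sensitivity of the tray score.** Assume that the score averages about 182 days; the supplied text does not fix the window for this trial.
- A patient with perfect days otherwise passes with 18 zero-scored days (164 / 182 = 0.901) and fails with 19 (163 / 182 = 0.896).
- A perfect patient who stops after month 5 scores 5 / 6 = 0.83 if later days count 0, and 1.00 if only observed days count.
- If only the final month were averaged, the same patient would score 0 or have no score to analyse.

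**3. Effect on the estimated difference.** Let p be the success rate among completers and d the share missing (S = SMASH, C = SC).
- Missing patients like completers: pS - pC.
- Missing patients all failures: pS(1 - dS) - pC(1 - dC).

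The second differs from the first by pC dC - pS dS, so its direction depends on which arm loses more would-be successes. D.8 gives no arm rates; 60% v 30% is assumed. The dropout figures are also assumed.

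| Dropout SMASH / SC | Like completers | All failures | Power, completers | Power, failures |
|---|---|---|---|---|
| 10% / 10% | 30 points | 54.0 - 27.0 = 27.0 | 85% | 79% |
| 15% / 5% | 30 points | 51.0 - 28.5 = 22.5 | 85% | 64% |
| 20% / 5% | 30 points | 48.0 - 28.5 = 19.5 | 84% | 52% |
| 5% / 20% | 30 points | 57.0 - 24.0 = 33.0 | 84% | 93% |

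Power is for a two-sided 0.05 test of two proportions at ICC 0.04. Under the failure rule all 96 per arm are analysed: 96 / (1 + 23 x 0.04) = 96 / 1.92 = 50 effective patients. Under the other rule, information is taken from completers only. The power columns compare the two rules; they are not a test of the plan's power statement.

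**4. When it would not matter.** At the adherence rates D.8 reports from its pilot (89% v 0%) with 10% missing per arm, failure scoring gives 0.90 x 89 = 80.1 v 0. The estimate falls by 8.9 points. At 89% v 10%, power is about 100% under either rule.

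**The case against.** The plan is not passive about missing data. Intent-to-treat analysis and multiple imputation apply at any level of missingness, dropout is examined by arm (D.10), missing data are reviewed twice monthly (D.9), phones or service plans are supplied against loss (D.4), and retention tactics are listed (D.12). Feasibility trials 2 and 3 retained 95% and 96%, so missingness may stay below 10%, though D.8 puts those trials at about 22 to 24 patients. All of this stands. A reader might infer that the sentence about a future trial is the plan's whole response to missing data; it is not. What remains is that none of these measures tests the imputation assumption.

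A reader might also infer that SMASH dropouts will be imputed as adherent completers, biasing the result towards SMASH. The documents do not say that. Entry criteria make every patient a failure on both outcomes at baseline, but the underlying scores vary. Daily tray scores and month-3 measurements could show decline before a patient leaves. The model is unstated, so the direction of bias cannot be asserted.

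Nor is a contradiction between zero scoring and imputation established. The zero rule is described for feasibility trial 1 and concerns missed doses. Observed misses could score 0 while absent outcomes are imputed, and Appendix 2 may say so. The zero rule cannot affect BP control, which is measured at a visit that a patient without a tray can still attend.

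**Conclusion.** The concern holds in a limited form. For both 6-month primary outcomes, the plan relies on multiple imputation with no sensitivity analysis for dropout related to adherence, and its threshold of more than 10% missing leads to no action in this trial. For the tray outcome alone, the supplied text leaves the scoring of silent days after stopping or withdrawal undefined, subject to Appendix 2.

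Under the assumed 60% v 30%, the plausible difference runs from 19.5 to 33 points across the dropout patterns shown, against 30 if missing patients resemble completers. If effects are as large as in the pilots, or dropout stays near 4% to 5% in both arms, the conclusion is unlikely to change.

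It is tempting to treat missing-as-failure as the safe analysis and require efficacy to hold under it. The 33-point case shows that it favours SMASH when SC loses enough more patients, so it should not be a gate. The attrition wording is a minor correction.

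**What to change.** Amend D.10 before outcomes by arm are examined:

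1. Keep intent-to-treat with multiple imputation as the primary analysis. Name the model, with month-3 outcomes and tray scores before dropout among the predictors.
2. For both 6-month primary outcomes, add (a) an analysis counting every missing outcome as failure and (b) a tipping-point analysis that varies success among missing patients separately by arm. Report whether the conclusion holds under each, without making (a) a condition for claiming efficacy.
3. For the tray outcome, state one rule, identical in both arms, for outage versus stopped use. Use the connection and reload data where they can tell the two apart, and say what happens where they cannot. If Appendix 2 already defines this, cite it.
4. In D.8, state that 192 retains 176 patients only up to 8.3% loss.

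The cost is some SAP wording and a few extra runs on data already due to be collected, with no new visits. The downside is that the result may look less robust.

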D.1. Design and Randomization: Subjects will be drawn from Fetter Health Care Network (FHCN). It is the sole FQHC center in the 4-county area (8 clinics) and provides ~60% of routine AA healthcare in the 4 county area.¹⁰⁷ A support letter from the FQHC network is included. EMR files indicated they have ~2,619 AAs (21-59 yrs old; mean age=45.3yrs) with sole diagnosis of uncontrolled HTN. We will use the 8 practice sites in a 2 arm RCT design (n=192) with clinic as unit of randomization and patient as unit of analysis. All primary healthcare providers across the 8 clinics have agreed to participate if selected. Each clinic has a minimum of 2 primary providers (at least 1 MD and 1 or more NPs and/or PAs per clinic). Thus, 2 providers per site will be recruited. Each will have 12 of their patients recruited (24 per clinic). Given our ~90% participation rate in previous FQHC studies^{25,108,109} and 93% SMASH participation rate, we anticipate no recruitment problems. The Medical University of South Carolina Family Medicine and Internal Medicine clinic population will be an additional recruitment resource if needed.

D.2. Participants: With consideration of the relevant biological variable of gender, we will recruit 192 AA 21-59 yr old uncontrolled HTNs with equal numbers of males and females that meet the following inclusion/ exclusion criteria: 1) SBP ≥ 140 mmHg on most recent clinic visit over last 12 mos and at BP screening and recruitment visits; 2) MPR < 0.85 over last 3 mos; 3) 24-hour SBP ≥ 130 mmHg (HTN cutoff) to help rule out white coat HTN.^{76,110} SBP used as selection variable since most AA HTNs < 60 have systolic or combination systolic/ diastolic HTN and for most patients, controlling SBP also results in DBP control;^{27,111,112} 4) no other known chronic diseases (e.g., diabetes, chronic kidney disease (GFR < 50 ml/1.73 m²/min), cancer, renal dialysis, heart attack, coronary artery bypass, arterial stent, substance abuse (e.g., > 21 drinks/week), psychiatric illness, Beck Depression Inventory¹¹³⁻¹¹⁵ > 13 , able to speak, hear and understand English; take own BP and meds; 6) owns smart phone with current data plan; 7) primary care MD's assent patient able to participate and 8) no planned pregnancy or vulnerable population (e.g., pregnant or nursing women, prisoners).

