Smashers will complete the values, beliefs and life goals questionnaire (VBG; see Appx. 14). Responses are used in a tree-structured algorithm to select tailored motivational and positive reinforcement SMS or voicemail messages based on previous day’s MA levels. Examples of motivational messaging based upon patients’ responses are provided in C.1.5 and Appx. 4. After 2 consecutive weeks of 100% MA (typically first 2-4 weeks), messages are switched from daily to a variable interval schedule averaging 2 messages/week. Cumulative MA graphs will be sent on their phones weekly during the 6-month trial (MA rate algorithm in Appx. 2). Automated SMS messages will remind subjects to self-measure BP every 3 days. After each BP session, the SMASH app provides audio and visual BP feedback, and opportunity to see BP averages charted over time and against JNC8 guidelines (screenshot example in Appx. 25).

SMASHers will receive 30-45 sec audio or SMS messages 2x/week on HTN facts (e.g., HTN is permanent, uncontrolled HTN is silent killer), importance of timely, consistent MA, tips on expressing questions /concerns with MD (e.g., side effects; examples in Appx. 26). SMASHers will have auto dial feature on their app for [name] (or TACHL service techs if needed) to address technology related issues should they arise.

D.5.b. Provider Level: SMASH primary providers will receive summary reports, designed by them, using patient ID#s every week based upon their preference (e.g., email; NexGen EMR with email reminder to view it; example in Appx. 27). They will receive email reminders for viewing generated reports as needed every 6 hrs for 24hr period. They (and the SC MDs) will receive the same summary charts of JNC8 BP management guidelines used by us in other studies^{22,23,25} (Example in Appx. 28). If a SMASHer’s mean BP exceeds thresholds (e.g., BP >180/ 105 or <100/75 mmHg) during a session, [name] will receive an SMS alert, call the patient and conduct the BP protocol again. If BP still exceeds thresholds, FQHC providers have requested their nurse managers be called to do a follow-up with the patient.

D.5.c. Enhanced Standard Care (SC) Protocol: Subjects whose practice site is randomized to the SC group will continue to use the tray with reminder functions disabled for another 6 months. To **help maximize rigor**

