In determining eligibility and subsequent enrollment, participants will have their resting BP measured by a research technician during an initial screening visit. If their average of the final 2 SBP readings \geq 140 mmHg and their 24-hr SBP \geq 130 mmHg, they will be eligible for the 1-month MA screening using the electronic medication tray with its reminder functions disabled. If, at the end of the 1-month MA screening, the adherence score is $<$ 0.85, they will participate in a baseline study evaluation that will again include measurement of resting BP and 24 hour BP. Those who again have uncontrolled HTN (resting SBP \geq 140 mmHg and 24-hr SBP \geq 130 mmHg) will be eligible for participation in the trial. Participants will have the resting BP and 24-hr BP monitoring performed again at months 3, 6, 12, and 18. At each evaluation, participants will complete a battery of questionnaires that have been purposely selected as having established psychometric properties for AAs and the age range of our cohort (see Appx 1, 7-21 for copies of questionnaires and additional psychometric properties than those presented in Table 3). Questionnaires will include measures of self reported MA, competence, autonomous motivation, health literacy, HTN knowledge, adverse events, med side effects, depression, sleep quality, stress, quality of life, patient satisfaction with provider). They will also complete several scales that assesses degree of satisfaction with study implementation and study/home evaluations, usability of the SMASH protocol ,app and wireless BP device or the enhanced SC group's educational materials, and potential barriers/facilitators of adherence. As part of standard care, all participants will have blood drawn at baseline and months 6, 12 and 18 to include TC, LDL, HgA1c and blood glucose levels. All subjects will wear an ambulatory BP monitor for 24-hr on several occasions over the course of the study. The combination of anthropometric evaluations, resting BP measurements, ambulatory BP measurements, and the majority of the questionnaires has been used in prior studies (e.g., HL 05662, HL 078216, and SMASH feasibility RCTs) and was not considered a burden by the subjects. All study materials will be de-identified so that only the subjects ID number will be associated with any collected data.

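### The adverse-event comparison uses an ordinary chi-square test although clinics are randomised, so its false-positive rate exceeds the nominal 5% if adverse events cluster by clinic

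*Combined protocol and SAP*

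**What the plan says.** D.1 sets up a cluster design, "with clinic as unit of randomization and patient as unit of analysis": 8 practice sites, two providers per site and 12 patients per provider, so 24 per clinic and 192 in all. D.8 works with "within-clinic sample sizes of 22 subjects for 4 clinics per group" and inflates the sample size for clustering. Its basis is "The ICC from our feasibility trials for primary outcomes of electronic med tray based MA and SBP was estimated at 0.04", within a considered range of 0.0 to 0.05.

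In D.10 the longitudinal models carry practice site as a random effect. The Introduction to the Revised Application says, in general terms, that clinic will be a random effect in the analytic model.

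The last paragraph on mediation analyses in D.10 turns to dropout and safety. Arms are compared on missing outcomes by logistic regression, with no terms listed. For safety, "Proportions within categories of AEs/SAEs for the SMASH vs. SC will be compared via chi-square analyses". Neither sentence mentions clinic. No significance level, ICC or expected event rate is given for the safety comparison.

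**The concern.** A chi-square test on pooled counts takes each patient as an independent observation. Here all patients of a clinic share an arm, providers, local recording habits and case mix. Any variation in event rates between clinics therefore feeds directly into the difference between arms. The test counts that variation as if it were treatment effect, and its p-values come out too small.

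At stake is a reported safety difference, in either direction, that reflects which four clinics were drawn. The same holds for the missing-outcome comparison if it is run without clinic. That comparison matters because D.10 relies on multiple imputation for missing end-of-study outcomes, and a misleading result on differential dropout would colour how the imputed results are read.

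**Working it through.** **The plan's own arithmetic.** D.8 gives no figure for safety, so only its sample-size frame can be reproduced. 8 × 22 = 176 and 8 × 24 = 192 match. A 10% increase on 176 gives 193.6, close to 192. At 22 per clinic and ICC 0.04 the variance inflation factor (VIF) is 1 + 21 × 0.04 = 1.84.

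**Inputs for the safety test.** Four clinics per arm and 24 patients per clinic (D.1). ICC 0.04, with range 0.0 to 0.05 (D.8, for adherence and systolic pressure; its use for adverse events is an assumption). Nominal level 5% two-sided, which D.8 states for Aim 1 only and which is taken here as the conventional level.

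**Formulas.** VIF = 1 + (m − 1) × ICC. Actual error of an unadjusted test = 2 × [1 − Φ(1.96 / √VIF)].

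| ICC | VIF, m = 24 | Actual error, m = 24 | Actual error, m = 22 |
|---|---|---|---|
| 0 | 1.00 | 5.0% | 5.0% |
| 0.01 | 1.23 | 7.7% | 7.5% |
| 0.02 | 1.46 | 10.5% | 10.0% |
| 0.04 | 1.92 | 15.7% | 14.9% |
| 0.05 | 2.15 | 18.1% | 17.1% |

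At ICC 0.04 and m = 24: 1.96 / √1.92 = 1.414, and 2 × [1 − Φ(1.414)] = 0.157.

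**Check by simulation.** The formula is a large-sample approximation, so it was tested with beta-binomial counts, 4 against 4 clinics of 24, ICC 0.04 and no true difference. The last column is a t-test on the eight clinic proportions with 8 − 2 = 6 degrees of freedom.

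| Event risk | Plain chi-square | With continuity correction | Clinic-level t-test |
|---|---|---|---|
| 2% | 11.0% | 3.7% | 2.9% |
| 5% | 14.3% | 8.3% | 4.4% |
| 10% | 15.8% | 10.7% | 4.8% |
| 20% | 15.7% | 12.2% | 5.1% |
| 30% | 16.1% | 13.1% | 5.0% |

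For risks of 10% to 30% the simulation agrees with the formula, and the clinic-level test holds its level. Near 2%, where many serious-event categories may lie, the inflation is smaller, and with a continuity correction it disappears. The plan does not say which version of chi-square it means.

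**The case against.** The size is conditional. No ICC for adverse events exists in the documents, the plan's own range starts at 0, and at 0 there is no inflation. No decision is tied to this test: the IRB judged the study minimal risk, and the data and safety monitoring plan sends serious events to the DSMB. These points stand, and they keep the matter minor. They do not make an unclustered test right for a clustered design.

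The general promise of a clinic random effect could be read to cover the missing-outcome regression, whose terms D.10 leaves open. That is fair, so for that model the request is to specify. The promise cannot cover the chi-square, which has no place for a random effect. A reader might also infer that the plan states an error rate and then exceeds it. It states none for safety; the comparison is with a conventional 5%.

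A stronger reading is tempting: that SMASH contact finds events which go unseen in standard care, so the counts are biased against SMASH. SMASH alone has home blood-pressure readings (D.5.a) and alert calls after out-of-range values, in which the project manager is to "call the patient and conduct the BP protocol again" (D.5.b). But adverse events are collected from all subjects at baseline and months 3, 6, 12 and 18 (Table 3; section 1.b of Protection of Human Subjects: "Questionnaires will include measures of self reported MA, competence, autonomous motivation, health literacy, HTN knowledge, adverse events"), and the technicians doing the evaluations are to stay blinded (section 1.a). All participants may contact study staff (section 2.a), and the retention calls in D.12 are not confined to one arm. Nothing says that a finding from an alert call is counted as an adverse event. The asymmetry in contact is documented; its effect on the counts is an inference, and its size cannot be computed from the documents.

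**Conclusion.** The point holds for the variance. The safety comparison in D.10 ignores the unit of randomisation, and no other section corrects it. With 24 patients per clinic, the actual error of a nominal 5% chi-square is about 16% for events that are not rare, if adverse events cluster with ICC 0.04. Over the plan's ICC range it runs from 5% to 18%. The result rests on an ICC borrowed from other outcomes and weakens for rare events. The figure of 16% should therefore be read as what the plan's own assumption would imply, not as the known error of this trial. The missing-outcome regression needs its clinic term stated.

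Detection bias is not established. It is a separate matter, since adjusting for clinic corrects the variance but would not correct unequal capture of events. The importance is low, but the text should be changed because the method does not match the design.

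**What to change.** Replace the chi-square sentence in D.10 with:

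> *Adverse-event proportions are compared between arms by a method that accounts for clinic and for the small number of clinics (a clinic-level summary test on 6 degrees of freedom, or a mixed model with a small-sample correction), and are reported as risk differences with 95% confidence intervals. Sparse serious-event categories are presented descriptively. The comparison of missing outcomes uses the same clinic adjustment.*

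The small-sample element matters: with eight clinics an uncorrected mixed model can itself be too liberal, and it can be unstable when events are few.

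An optional sensitivity comparison may be limited to events elicited at the scheduled evaluations in both arms. All events from any source should stay in the main safety tables, because patients who die, are in hospital or drop out may not complete the visit questionnaire, and a main comparison restricted to it could lose serious events.

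Cost: one sentence and one model. The main change needs no new data. The sensitivity comparison needs the source of each event to be recorded, which the documents do not describe. Intervals widen: at ICC 0.04 by √1.92 = 1.39 for clustering, and by 2.447 / 1.960 = 1.25 for using t on 6 degrees of freedom, together about 1.73 times the unadjusted width.
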